7.5.1.1 Sensitivity Analyses for Primary Efficacy Endpoint

In order to assess the robustness of the effectiveness of apixaban relative to standard care, the following sensitivity analyses will be performed for the primary efficacy endpoint:

[figure not shown]
- An analysis will be performed using the mITT Population.

- An analysis will be performed for all randomized subjects with missing primary endpoint or non-evaluable imaging data to be assessed via multiple imputation using 1000 repetitions, with imputation of events for patients with missing data in both treatment groups based on the event rate observed from the corresponding stratum in the standard-of-care arm
- If results from the primary efficacy analysis show a significant difference between treatment groups, then a “tipping point” analysis will be performed with a non-stratified analysis. In each analysis, subjects with missing data in the standard-of-care arm will be assumed to be event-free, while progressively more subjects with missing data in the apixaban arm will be assigned with an event, up to the limit of the number of subjects with missing data in the apixaban arm. The number of subjects in the apixaban arm imputed with event that would change the result from significant to non-significant would be noted.
- An analysis will be performed based on the Evaluable Population, if at least 10% of subjects have a relevant protocol deviation.

7.5.2 Secondary Efficacy Analysis

The key secondary objective is to assess the effect of prophylactic apixaban versus no administration of systemic prophylactic anticoagulant during induction chemotherapy, on single adjudicated endpoints of non-fatal asymptomatic DVT, symptomatic DVT, PE, and CVST; and VTE-related-death during intended treatment period.

Two-sided 95% CI for the relative risk (p_a/p_e) will be reported for the key secondary efficacy endpoint. The nominal p-value associated with the tests will also be reported.

7.5.4 Subgroup Analysis

Rates for the primary efficacy endpoint will also be summarized by treatment group and subgroups listed in Table [Table 6.3-1](#). Ninety-five percent (95%) CIs for the ratio of event rates will be computed based on Mantel-Haenszel’s method stratified by the stratification factor(s) as applicable

The analyses will be performed using events occurring during the Intended Treatment Period and for the Primary endpoint (when summarizing the primary efficacy endpoint). If the value of the

grouping variable cannot be determined for a subject, the subject will be excluded from the corresponding subgroup analysis. For each subpopulation analysis, if, in any treatment group, the number of subjects is ≤ 10 for a subgroup, then the grouping variable will not be included in the test of treatment by subpopulation interaction.

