3.3.1 Inclusion Criteria

1. Signed Written Informed Consent

- a. Signed written informed consent obtained from subject's legally acceptable representative (parents or guardians) according to local regulations and if mentally capable, assent from subject if required locally

2. Target Population

- a. New diagnosis of de novo ALL, or lymphoblastic lymphomas (T or B cell)
- b. Planned 3-4 drug systemic induction chemotherapy with a corticosteroid, vincristine and a single dose or multiple doses of asparaginase, with or without daunorubicin
- c. Patients with mixed-phenotype acute leukemia (MPAL) who will be treated with ALL induction chemotherapy as described above (Inclusion 2b) are also eligible
- d. Functioning CVAD, defined as no known mechanical problem and including external tunneled CVAD, implantable ports, and peripherally inserted central catheters (PICC) placed in a new location between Day -7 and Day 4±3 of induction chemotherapy and planned to remain in place until at least Day 29±5 days of induction. The CVAD must be

inserted prior to the start of study medication and could be inserted prior to signing informed consent as part of standard of care.

Note: The CVAD can be replaced if it is a planned replacement (eg, it is allowed to have a PICC at the time of enrollment that will be changed to a more permanent line later in induction); and it is allowed if a CVAD is not in place at the time of enrollment as long as it is in place before apixaban starts.

- e. Not applicable per protocol amendment 04
- f. Able to tolerate oral medication or have it administered via an NGT or GT tube.
- g. Subject Re-enrollment: This study permits re-enrollment of a subject that has previously failed screening but currently meets entry criteria. If re-enrolled, the subject must be re-consented and receive a new patient identification number.

3. Age and Reproductive Status

- a. Males and females, age ≥ 1 year (365 days) to < 18 (17 years and 364 days) years at the time of consent.

Females of reproductive potential (FRP) must have a negative serum or urine pregnancy test (minimum sensitivity 25 IU/L or equivalent units of HCG) at screening.

For all FRP that will be inpatients from consenting to the first dose of apixaban, a negative pregnancy test must be recorded in the subject's hospital chart prior to receiving the first dose of apixaban.

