5 SAMPLE SIZE AND POWER

With a total of approximately 500 randomized subjects allocated with 1:1 ratio to the systemic thromboprophylaxis with apixaban or no systemic anticoagulant prophylaxis (control) group, there is more than 80% power to demonstrate superiority at a one-sided 0.025 level, assuming the true event rates of primary endpoint (composite of non-fatal asymptomatic and symptomatic DVT, pulmonary embolism (PE), and CVST; and VTE-related-death) are 17% and 8.5% in the control and the apixaban groups, respectively. Sample size estimation is based on Pearson's chi-square test.

Additionally, there is more than 80% power to demonstrate superiority at a one-sided 0.025 level, assuming the true event rates are 20% and 10% in the control and the apixaban groups, respectively with analyses that assume that 20% of the subjects will be excluded from the primary analysis due to either early dropout without end-of-treatment imaging evaluation or non-evaluable end-of-treatment imaging measurement in the calculation.

Randomization will be stratified by age groups as <10 years or ≥ 10 to <18 years, to reflect the major peaks of disease prevalence and risk stratification criteria for acute lymphoblastic leukemia (ALL) in children.

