Obesity	Non-obese (less than the 95th percentile of age- and sex-specific BMI)* Obese (Equal to or greater than the 95th percentile of age- and sex-specific BMI)*
ALL risk	Standard risk (WBC count less than 50,000/ μ L and age 1 to younger than 10 years) High risk (WBC count 50,000/ μ L or greater and/or age 10 years or older)
Central line	Peripherally inserted central catheters (PICC) lines All tunneled lines (including totally implanted devices/ports) All others (“non-tunneled line” and “other” from below, which will likely number 0 or at least a very small number of patients)

* The definition that is based on Central for Disease Control and Prevention criteria

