7.1 General Methods

Descriptive summaries will be presented for continuous variables using number of subjects (N), mean, standard deviation (SD), median, minimum and maximum. Descriptive summaries for categorical variables will utilize counts and percentages.

Adverse events will be coded according to the most recent Medical Dictionary for Regulatory Activities (MedDRA) version. Adverse events will be summarized according to the MedDRA coded Preferred Terms (PT) by System Organ Class (SOC). Previous and concomitant medications will be coded using the WHO Drug Dictionary version.

Unless otherwise specified, baseline is defined as the last non-missing result with a collection date-time prior to the date-time of the randomization.

Testing for Treatment by Subpopulation Interaction

For efficacy subgroup analyses, Wald's chi-square test will be used to test whether treatment has a statistically significantly different ($p < 0.1$) effect on the event rate of an endpoint across subgroups (e.g. male, female) based on a logistic model with terms for treatment, stratification variable age, subpopulation, and treatment by subpopulation interaction.

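### SAP 7.5.4: 1 to 21 children in the residual 'All others' level would cancel the central-line interaction test, however large the PICC and tunneled levels are

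*SAP*

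**What the plan says.** SAP 7.1 plans, for the efficacy subgroup analyses, a Wald chi-square test of interaction at p < 0.1. It comes from a logistic model with terms for "treatment, stratification variable age, subpopulation, and treatment by subpopulation interaction". That is one test per grouping variable.

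SAP 7.5.4 adds a small-cell rule: if, in any arm, "the number of subjects is ≤ 10 for a subgroup, then the grouping variable will not be included in the test" of interaction. The trigger is a single level in a single arm. The consequence falls on the whole variable. A separate clause excludes a child whose value of the grouping variable cannot be determined.

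SAP Table 6.3-1 gives central line three levels: PICC, all tunneled lines (ports included), and 'All others'. Of the last it says "which will likely number 0 or at least a very small number of patients".

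Protocol 3.3.1, criterion 2d, describes eligible devices as "including external tunneled CVAD, implantable ports, and peripherally inserted central catheters (PICC) placed in a new location". The word 'including' leaves room for other devices.

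The descriptive results do not depend on the rule: "Rates for the primary efficacy endpoint will also be summarized by treatment group and subgroups listed in Table" 6.3-1, with 95% confidence intervals for the rate ratio.

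**The concern.** The SAP defines a level, forecasts that it will hold few or no children, and then applies a rule under which a level with few children removes the variable from the test. A small-cell rule is meant to avoid unstable estimates from sparse cells. Here it would also stop the comparison between two levels that may each be well filled. A handful of children in a residual category would decide whether the test is run.

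At stake is the only formal comparison of the treatment effect across line types. A functioning central line is an entry requirement, and the sponsor lists line type as a subgroup of interest. The visible text contains no provision to pool, omit or exempt the residual level.

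**Working it through.** **Inputs.** About 500 children randomized 1:1 (SAP 5), so 250 per arm. The trigger is 10 or fewer in a level in any arm (SAP 7.5.4). Planning risks are "17% and 8.5% in the control and the apixaban groups, respectively" (SAP 5). The interaction test is at p < 0.1 (SAP 7.1). The documents give no distribution of line types, so every share below is an assumption.

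**The plan's own power figure.** For Pearson's chi-square at one-sided 0.025, 17% versus 8.5% with 250 per arm gives 81.5%. For 20% versus 10% with 20% excluded (200 per arm) it gives 80.2%. Both agree with the stated figure of more than 80%. The documents give no power for any interaction test.

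**When the rule must trigger.** Both arms exceed 10 only if each has at least 11, so the level needs 11 + 11 = 22 children. For every total T from 1 to 21 (0.2% to 4.2% of 500), at least one arm has 10 or fewer, and the variable is dropped with certainty.

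**Above 21.** With T such children among 500 split 250/250, the number in one arm is hypergeometric:

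| T | P(both arms > 10) | P(test cancelled) |
|---|---|---|
| 21 | 0 | 1 |
| 22 | 0.172 | 0.828 |
| 25 | 0.588 | 0.412 |
| 30 | 0.911 | 0.089 |

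**How likely is a total of 1 to 21?** This cannot be read from the documents. As illustration only, let p be the true share of 'All others'. Then P(empty) = (1 − p)^500, and P(non-empty and rule triggered) = 1 − P(empty) − [P(Bin(250, p) > 10)]².

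| p | P(empty) | P(non-empty, triggered) |
|---|---|---|
| 0.1% | 0.61 | 0.39 |
| 0.5% | 0.08 | 0.92 |
| 1% | 0.007 | 0.99 |
| 5% | about 0 | 0.50 |

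The 5% row means about 25 children, which hardly fits the SAP's own forecast.

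**What a retained two-level test could detect.** Take PICC versus tunneled, 250 per arm, control risk 17% in both line types and two-sided alpha 0.10, with no age term. On the log-odds scale:

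- d = |logOR(PICC) − logOR(tunneled)|
- SE² = sum over the four arm-by-line cells of 1/[n·r(1 − r)], where r is the cell risk
- power = Φ(d/SE − 1.645) + Φ(−d/SE − 1.645)

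Example: PICC share 50%, relative risks 0.4 and 0.6. Each cell has 125 children, and the apixaban risks are 0.17 × 0.4 = 0.068 and 0.17 × 0.6 = 0.102. Then d = 0.443 and SE² = 2(0.0567) + 0.1262 + 0.0873 = 0.327, so SE = 0.572 and d/SE = 0.774. Power is Φ(−0.871) + Φ(−2.419) = 0.192 + 0.008 = 0.20.

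Ranges over which line type has the stronger effect:

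| PICC share | RR 0.4 v 0.6 | RR 0.5 v 1.0 |
|---|---|---|
| 10% | 0.13-0.14 | 0.22-0.26 |
| 20-50% | 0.16-0.20 | 0.31-0.45 |

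A simulation with the age term in the model (1,500 runs per setting, PICC share 20% and 50%, assumed 30% aged 10 or over with 1.5 times the risk, average control risk 17%) gave 0.10-0.20 and 0.28-0.46.

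**The case against.** **No PICC-versus-tunneled test is planned.** A reader might infer that a dedicated two-level contrast is being cancelled. The documents do not support that. SAP 7.1 plans one interaction test per grouping variable, which for central line has 2 degrees of freedom if all three levels are populated. The power figures above therefore describe the test that could be kept, not the one written. It remains true that dropping the variable removes the only formal comparison of effect by line type.

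**The level may be empty.** The devices named in Protocol 3.3.1 all fall in the first two levels, and the SAP's first expectation is zero. A reader might infer that zero also cancels the test, because 0 is at most 10. That is a weak reading. A level with nobody in it adds no parameter to the model, so the natural result is a two-level variable. But the SAP's forecast also allows for a few children, and a few are enough to cancel.

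**The rule is a sensible guard.** It is, against unstable Wald tests in tiny cells. Leaving out only the residual level gives the same protection.

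**Other variables are exposed too.** Race, region or the youngest age band could also have a sparse level. Central line is the one variable for which the SAP itself predicts this, which is why the point is confined to it.

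**Part of the text is not visible.** Table 6.3-1 refers to a list of line categories that cannot be seen, and the visible numbering passes from 7.5.2 to 7.5.4. An exception there cannot be excluded.

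**Conclusion.** The point holds as a minor one. Under SAP 7.5.4 as written, 1 to 21 children in 'All others' cancel the central-line interaction test regardless of how many children have PICCs or tunneled lines. That bound is exact for two arms and rests on no assumption about shares. Whether a total in that range will occur is not known from the documents, so the probabilities by assumed share are illustrative and carry no weight in the conclusion.

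A reader might infer that evidence by line type is lost, or that the main result is touched. Neither follows. Rates and rate-ratio intervals by line type are still reported, the test is exploratory, and the primary conclusion does not depend on it. The power of the two-level test is low to modest under the assumed shares and effects, so little information is lost even when the rule triggers.

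**What to change.** Add one sentence to SAP 7.5.4, before line-type counts by arm are known:

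> For central line, if All others has ≤ 10 subjects (including 0) in either treatment group, that level is shown descriptively and left out of the interaction test, which then compares PICC with all tunneled lines, provided each has > 10 subjects in both treatment groups.

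This keeps the small-cell safeguard for the two levels being compared, settles the empty-level case, and leaves the rule for the other grouping variables as it is. It needs no new data. The cost is that the few children in 'All others' are left out of that one test, and that one low-powered exploratory test is run which the present wording would suppress.

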7.6 Safety

Safety presentations will be based on the Safety Population during the Treatment Period. In addition to the analyses and summaries based on the Treatment Period, the analyses and summaries for bleeding outcomes, AEs, SAEs, SAEs with death outcome, AEs leading to discontinuation, events of special interest, elevations in liver function tests (LFTs), and decreases in platelet counts will also be performed based on the On-Treatment period for apixaban treated subjects only.

For analyses of events during the Treatment Period, non-serious adverse events will be included in analyses if their onset occurs during the Treatment Period, or within 2 days after the end of the Treatment Period. Serious adverse events will be included in analyses if their onset occurs during the Treatment Period, or within 30 days after the end of the Treatment Period. For analyses of events during the On-treatment Period, events will be included if they occur during the On-treatment period, or within 2 days (non SAE) or 30 days (SAE) after the end of the On-treatment period. All events will be listed.

7.6.1 Bleeding Events

7.6.1.1 Bleeding Endpoints

For the primary safety endpoint (major bleeding) and the secondary safety endpoint (composite of major bleeding and CRNMB) during the treatment period, the event rate, 95% CI for event rate, relative risk, 95% CI for relative risk and nominal p-value will be displayed. To construct nominal p-values and 95% CI for relative risk, the Cochran-Mantel-Haenszel test stratified by age groups of < 10 years and ≥ 10 years old will be used at the one-sided $\alpha=0.025$ level. Construction of CIs for single event rates will be based on the Agresti Coull method.

All confirmed bleeding events will be listed, indicating the subject id, treatment group, age, gender, race, date of last dose of study drug prior to event and day of event relative to start of dosing.

7.6.1.2 Other Bleeding Related Safety Endpoints

For the CRNMB and minor bleeding during treatment period, event rate, 95% CI for event rate, relative risk, 95% CI for relative risk and nominal p-value will be displayed.

Number of platelet transfusions needed during the study will be summarized, and summary statistics including number and percentage will be presented by treatment group.

All bleeding events will be listed, including the subject id, treatment group, age, gender, race, event type, and reported event date.

7.6.2 Adverse Events

All AEs will be coded and grouped into Preferred Terms (PT) by System Organ Class (SOC), using the Medical Dictionary for Regulatory Activities (MedDRA). Listings and summaries will be based on the resulting SOCs and PTs.

The incidence of bleeding-related AEs during the Treatment Period will be summarized by SOC, PT and treatment group.

All reported AEs and SAEs will be listed, indicating the subject id, treatment group, age, gender, race, day of onset relative to start of dosing, resolution date, investigator-assessment of relationship to study drug, investigator-assessment of intensity of event, action taken regarding study drug and whether treatment was required for the event.

Summary information (the number and percentage of subjects) regarding AEs (for serious and non-serious events) will be tabulated by SOC, PT and treatment group for:

- all events
- deaths
- related events
- all events categorized by intensity

The frequency of subjects discontinuing study drug due to AEs will be tabulated by SOC, PT and treatment group.

Most common AEs (reported in more than 5% of subjects in any treatment group) will also be summarized by PT and treatment group.

Laboratory AEs are laboratory results identified by the Investigator as AEs and thus reported on the AE pages of the CRF. Any such AE occurring during the Treatment Period will be included in the respective AE summaries.

7.6.3 Laboratory Data

The frequency of subjects with laboratory marked abnormalities (MAs) during the Treatment Period based on pre-specified criteria will be tabulated by treatment group, for each analyte.

Laboratory measurements (for liver function only) and their changes from baseline will be summarized at baseline and at the end of study by treatment group.

Shift analysis will be performed to evaluate qualitative changes that occurred during the Treatment Period. Shift tables (for liver function only) will display, by treatment group, the frequency of subjects with the following combination of values at baseline and during the Treatment Period:

- no change (low to low: L-L, normal to normal: N-N, high to high: H-H)
- abnormal to normal (low to normal: L-N, high to normal: H-N)
- normal to abnormal (normal to low: N-L, normal to high: N-H)
- abnormal to abnormal (low to high: L-H, high to low: H-L),

where low refers to values that are $<LLN$, high refers to values that are $>ULN$ and normal refers to values in-between the normal limits. Two sets of shift tables will be presented:

- one for labs with MA criteria based on high values (regardless of whether the MA criteria also considers low values) - the post-dose value considered for the tabulation will be the largest value obtained during the Treatment Period;
- another for labs with MA criteria based on low values (regardless of whether the MA criteria also considers high values) - the post-dose value considered for the tabulation will be the smallest value obtained during the Treatment Period.

In addition, liver-related elevations and discontinuations will be tabulated by treatment group. The tabulation will include the number and proportion of subjects with

- post-dose elevation of AT $>3 \times ULN$ (AT refers to either one of ALT or AST)
- post-dose elevation of AT $>5 \times ULN$
- post-dose elevation of AT $>10 \times ULN$
- post-dose elevation of AT $>20 \times ULN$
- post-dose elevation of conjugated bilirubin $>2 \times ULN$
- post-dose elevation of AT $>3 \times ULN$ and conjugated bilirubin $>2 \times ULN$ on the same date
- Liver-related discontinuations

The number and proportion of subjects with post-dose elevations of AST, ALT, conjugated bilirubin, ALP, or CK will also be tabulated by treatment group including:

- AST elevations $>3 \times ULN$, $>5 \times ULN$, $>10 \times ULN$, or $>20 \times ULN$
- ALT elevations $>3 \times ULN$, $>5 \times ULN$, $>10 \times ULN$, or $>20 \times ULN$
- AST or ALT elevations $>3 \times ULN$, $>5 \times ULN$, $>10 \times ULN$, or $>20 \times ULN$
- both AST and ALT elevations $>3 \times ULN$, $>5 \times ULN$, $>10 \times ULN$, or $>20 \times ULN$ on the same date
- ALP elevations $>2 \times ULN$
- CK $>10 \times ULN$

Similar tabulations for the number and proportion of subjects with elevations of AST, ALT, total bilirubin, ALP, or CK as described in the previous paragraph will be presented by treatment group and by nominal visit (including baseline).

The following considerations apply to all liver-related laboratory tabulations described above:

- AT elevation refers to ALT or AST elevations regardless of whether they occurred concomitantly
- elevations will be counted if they occur during the Treatment Period; Only values that meet the criteria and are larger than the baseline value will be included in the tabulations. If baseline

value is missing then all values for that particular lab that meet the criteria will be included in the tabulations.

- values will be counted towards the categories of “AST and ALT elevations”, or “AT and Total Bilirubin elevation” if both AST and ALT or both AT and Total Bilirubin, respectively, meet the criteria and at least one of the values in the component is larger than the baseline value.
- values will be counted towards the categories of “AST or ALT elevations” if either AST meets the criteria and is larger than the AST baseline value or ALT meets the criteria and is larger than the ALT baseline value.
- For each subject and lab or lab combination, the largest value measured during the Treatment Period will be counted for the Treatment Period summaries that do not take nominal visit into consideration
- For each subject and lab or lab combination, the largest value measured within each visit window during the Treatment Period will be counted for the summaries by nominal visit.

The number and proportion of subjects with decreased platelet counts to $<20,000/\text{mm}^3$ will be tabulated by treatment group and by nominal visit (including baseline) and by treatment group for all measurements during the Treatment Period. The following considerations apply to these summaries:

- decreases will be counted if they occur during the Treatment Period; only platelet counts that meet the criteria and are smaller than the baseline count will be included in the tabulations. If baseline value is missing then all platelet counts that meet the criteria will be included in the tabulations
- for each subject, the smallest platelet count obtained during the Treatment Period will be counted for the Treatment Period summaries that do not take nominal visit into consideration
- for each subject, the smallest platelet count obtained within each visit window during the Treatment Period will be counted for the summaries by nominal visit.

[figure not shown]

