3.4.2 Other Restrictions and Precautions

Based on pre-clinical and clinical data, apixaban might increase the likelihood of bleeding. Hence, subjects with platelet counts < 20,000 /microL, undergoing a lumbar puncture, or having surgical procedures, including a bone marrow aspirate and dental procedures should be instructed to inform their doctors about these procedures, and proper cautions should be taken by the investigator to reduce potential risk of bleeding (see [Section 4.5.2](#) for instruction).

Apixaban should not be administered if the platelet count is < 20,000/ microL. A subject may be transfused platelets per investigator's clinical judgement but may not be transfused solely to meet entry criteria.

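### The platelet table in SAP 7.6.3 is to have a baseline row, but its lower-than-baseline counting rule stops that row showing who starts below 20,000 and leaves out children who stay below 20,000 without falling further.

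*SAP*

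**What the plan says.** SAP 7.6.3 introduces the table as "The number and proportion of subjects with decreased platelet counts to" below 20,000/mm³. It is to be "tabulated by treatment group and by nominal visit (including baseline) and by treatment group for all measurements during the Treatment Period". The SAP then states "The following considerations apply to these summaries" and gives these rules:

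- Period: "decreases will be counted if they occur during the Treatment Period".
- Comparison with baseline: "only platelet counts that meet the criteria and are smaller than the baseline count will be included in the tabulations". If the baseline count is missing, every count below 20,000 is included.
- Value used: the smallest count in the Treatment Period for the overall summary, and the smallest in each visit window for the by-visit summary.

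No exemption is written for the baseline row, and no denominator is given.

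Three other places in the SAP bear on this. Sections 7.1 and 8.2 define baseline as the last value before randomization. Table 8.3-1 lets the baseline window run through the day of randomization. Section 6.1 starts the Treatment Period on that same day.

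In the protocol, 20,000 is the threshold for giving the drug. Section 3.4.2 reads "Apixaban should not be administered if the platelet count is" below 20,000/microL. The count must be at or above 20,000 within 24 hours before the first dose, but sections 3.3.1 and 3.3.2 list no platelet minimum for entry.

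The by-visit liver tables in SAP 7.6.3 are also planned with a baseline row, under a parallel rule: "Only values that meet the criteria and are larger than the baseline value will be included in the tabulations".

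**The concern.** The section asks for a baseline row and then applies a rule that a baseline value cannot satisfy. A programmer must either print a row that is empty whatever the children's starting counts, or make up an exemption.

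The same rule governs the later rows. A child who enters below 20,000 and stays there, without dropping under the starting value, is left out of the numerator at every visit and overall.

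The threshold matters in this trial. It governs whether apixaban may be given, and major bleeding is the primary safety endpoint. A reader would naturally use this table to see how many children in each arm were below 20,000, and when. The omissions fall entirely on children who were already below it at randomization.

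**Working it through.** The plan states no figure for this table, so there is nothing to reproduce. The check applies the rule to cases and then illustrates its possible size.

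**Rule.** Let B be the baseline count and m the smallest count in the visit window that lies in the Treatment Period. The child is counted if m < 20,000 and m < B, or if m < 20,000 and B is missing.

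**Baseline row.** Putting m = B, the condition B < B is never true. Running the rule over baseline values from 1,000 to 300,000 gave none counted. The row can be non-zero only through a different count on the day of randomization, because that day belongs to both the baseline window and the Treatment Period:

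- 15,000 earlier that day, then 25,000 as the last value before randomization (B = 25,000): counted.
- B = 25,000, then 18,000 later that day: counted.
- B missing, 15,000 later that day: counted.

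None of these measures how many children start below 20,000.

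**Later rows.**

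| Baseline | Four later visits | Visits below 20,000 | Visits counted | Counted overall |
|---|---|---|---|---|
| 15,000 | 15,000; 16,000; 18,000; 19,000 | 4 | 0 | no |
| 15,000 | 14,000; 18,000; 19,000; 19,000 | 4 | 1 | yes |
| 25,000 | 19,000 at each | 4 | 4 | yes |
| missing | 15,000; 16,000; 18,000; 19,000 | 4 | 4 | yes |

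The first and last rows have the same on-study course and are reported in opposite ways, only because one baseline is missing.

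**Possible size at Day 8.** All inputs here are assumed. Take log-normal counts with log SD 1.0 at baseline and 0.8 at Day 8, and correlation 0.5. The share below 20,000 is Φ(ln(20/median)/SD), with medians in 10⁹/L. The share counted, P(Day 8 < 20 and Day 8 < baseline), was obtained by simulation.

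- Setting A (medians 60 and 40): baseline Φ(−1.10) = 13.6%. Day 8 below, 19.36%; counted, 16.03%; missed, 1 − 16.03/19.36 = 17%.
- Setting B (medians 45 and 35): baseline Φ(−0.81) = 20.9%. Day 8 below, 24.24%; counted, 18.55%; missed, 1 − 18.55/24.24 = 23%.

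Varying the correlation from 0.3 to 0.7 moves the missed share across 13% to 30%.

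**Possible size over the whole period.** One count below baseline is enough to be included, so the shortfall shrinks as counts accumulate. With Day 8's distribution at every visit, and visits independent given baseline (correlation 0.5), the missed share is about 8% (A) and 11% (B) with four counts, and about 3% and 5% with eight.

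**The case against.** The strongest defence is that the table is worded as a count of decreases. A child going from 12,000 to 14,000 has not decreased, and a worsening-from-baseline filter is an ordinary treatment-emergent convention, used for the liver tables as well. That stands, and the filter is legitimate for that purpose. It does not rescue the baseline row, because a worsening filter and a baseline row cannot coexist.

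Several stronger readings are tempting, and the documents do not support them.

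- *The baseline row is always zero.* Not quite: same-day counts and the missing-baseline exception can enter it, as shown above.
- *Persistently low children are reported as not below 20,000.* Strictly, they are reported as not having decreased to below it. They read as not below only if they stay in the denominator, which the SAP does not state.
- *Baseline imbalance is hidden.* SAP 7.3.2 summarizes baseline platelet count by arm and age stratum and says imbalances will be reviewed; SAP 7.1 adds median, minimum and maximum. What is missing is the share below 20,000.
- *A fixed fraction of cases is lost.* No platelet distribution is given, and the overall shortfall depends on how often counts are taken. Protocol 5.3.7 asks for counts at least twice a week in children who are below 20,000 or expected to fall there, which would make that shortfall smaller.

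Other planned output covers part of the gap. Marked abnormalities are tabulated for each analyte, but the criteria are not given in the SAP, so their coverage of platelets below 20,000 is unknown. Platelet transfusions are summarized by arm in SAP 7.6.1.2, and Protocol 6.3 has laboratory abnormalities that lead to interruption or transfusion recorded as adverse events. Shift tables are for liver function only. None of these clearly gives the share below 20,000 at baseline or by visit.

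SAP section 9 defers table details to the Data Presentation Plan. That plan can settle layout, but the counting rule is set in the SAP itself.

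**Conclusion.** The contradiction is real and follows from the SAP's own wording. Apart from same-day counts of the kinds listed, the baseline row is zero and cannot show how many children start below 20,000. The by-visit and overall rows understate how many are below the threshold, because they omit those who stay below it at or above their baseline; the missing-baseline exception adds an inconsistency between children with identical courses.

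This rests on two readings: that the counting rules apply to both platelet summaries, as the SAP says, and that children can be randomized below 20,000, as the eligibility lists allow. The 17% to 23% at Day 8 is illustration under assumed distributions and should not be quoted as an estimate for this trial.

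Importance is modest. The table is descriptive, with no test or decision attached. The parallel defect in the liver tables is minor: liver values are summarized at baseline, the shift tables show children who are high at both times, and Protocol 3.3.2 excludes ALT or AST above 5 times the upper limit, so the highest baseline categories should be nearly empty anyway.

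**What to change.** In SAP 7.6.3:

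1. Tabulate all children with platelets below 20,000 at each nominal visit. For the baseline row use the baseline value as defined in 8.2, exempt from both the Treatment Period and the smaller-than-baseline conditions.
2. Keep below 20,000 and lower than baseline as a separate row labelled treatment-emergent, with the missing-baseline rule stated beside it.
3. State the denominator for each row, for example children with a count in that visit window.
4. Exempt the baseline row of the by-visit liver tables from the larger-than-baseline rule in the same way.

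The cost is SAP wording and one extra row. No new data are needed, and nothing changes in the conduct of the trial.
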